### Sample size rationale

Sample sizes were calculated to yield at least 90% power to detect a 15 percentage point difference (e.g., 45% vs. 60%) between baseline condition 1 and the other 4 conditions, with  $\alpha=0.05$  (GPower 3.1.9.4).

Stopping rule

Participants will be recruited until a sample size of 1000 is achieved.

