## Hypotheses

Hypothesis 1: When centers must present information on their transplant success rate only, lay evaluators will respond by selecting hospitals with higher transplant success. However, if information presented on transplant outcomes is stratified by the number and quality of donors used, or displayed in addition to total survival rates, then participants will respond by selecting hospitals with higher organ acceptance rates rather than the hospital with higher transplant outcomes. Hypothesis 1a: Preference for the non-selective transplant center will be lower (than for the selective center) in condition 1 (baseline: combined transplant survival only), compared to the other 4 conditions. That is, a higher proportion of participants will prefer the non-selective center over the selective center in conditions 2, 3, 4, and 5, relative to condition 1. Hypothesis 1b: There will be a main effect of viewing total survival, such that in conditions 2 and 4 (when total survival is displayed), participants will prefer the non-selective center over the selective center, relative to the baseline condition 1. Hypothesis 1c: There will be an additional main effect of viewing stratified transplant survival, such that in conditions 3 and 4 (when transplant survival is stratified by number and quality of donor hearts accepted at each center) participants will prefer the non-selective center over the selective center, relative to the baseline condition 1. Hypothesis 1d: There will be an interaction effect between total and stratified transplant survival, such that when participants view both stratified transplant survival and total survival outcomes together, preference for the non-selective center is higher relative to preferences at baseline (condition 1), but not higher relative to preferences when total survival information is added to the display (condition 2) or stratified transplant survival

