### Sample size

Our target sample size is 1000 participants. We expect that this will amount to approximately 200 participants per condition, although due to the nature of the randomization technique used (Qualtrics randomizer function), we may end up with slightly more or slightly less than 200 per condition.

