## Analysis Plan

Statistical models

To test Hypotheses 1a /1b/1c/1d, we will use a binomial logistic regression analysis. The two categorical independent variables will be 'total survival displayed' and 'stratified transplant survival'; the model will also include an interaction term of these two variables. The dependent variable is binary choice of hospital. -We will test whether the main effect of "total survival displayed" is statistically significant and in the predicted positive direction. -We will test whether the main effect of "stratified transplant survival" is statistically significant and in the predicted positive direction. -We will test whether the interaction effect "total\*stratified" is statistically significant in the predicted negative direction. To test Hypothesis 2, we will conduct a causal mediation analysis to determine whether information display had a mechanistic effect on hospital choice through our proposed mediator. We will estimate the average causal mediation effect (ACME), average direct effect (ADE), and the total effect. The ACME is the effect of each information display condition (total, stratified, or total\*stratified) on the outcome of hospital choice (selective vs. non-selective), mediated through the hypothesized mediator (the importance of "getting any heart" at each hospital when considering the choice). The remaining effect of information display on hospital choice that is not mediated through the hypothesized mediator represents the ADE. The entire effect of the information display on hospital choice via the hypothesized mediator and the direct effect is the total effect. The proportion of the total effect that is accounted for by the ACME is called the proportion mediated.{Imai, 2010}. Analyses will be performed using the "mediation" package in R (The R Foundation for Statistical Computing).{Tingley, 2014}. We will generate 95% confidence intervals by using 1000 bootstrap simulations. The unstandardized point estimate of the ACME and its 95% confidence intervals will be interpreted. -A significant ACME for "total survival displayed" would suggest that displaying total survival works via increasing the perceived importance of "getting any heart" to increase preference for the non-selective hospital. If the ACME is non-significant, we will identify where the causal path breaks down. -A significant ACME for "stratified transplant survival" would suggest that stratifying transplant survival by number and quality of accepted donors works via increasing the perceived importance of "getting any heart" to increase preference for the non-selective hospital. If the ACME is non-significant, we will identify where the causal path breaks down. -A significant ACME for "total survival displayed\*stratified transplant survival" would suggest that the combination of displaying total survival and stratifying transplant survival by number and quality of accepted donors works via increasing the perceived

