
importance of "getting any heart" to increase preference for the non-selective hospital. If the ACME is non-significant, we will identify where the causal path breaks down. To test Hypothesis 3, we will use a binomial logistic regression analysis with a contrast test for a difference in effect size between conditions 4 and 5.

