#### *No files selected*

##### Transformations

Logistic regression analysis: The categorical predictor "total survival displayed" will be dummy coded (0=not displayed, 1=displayed), with 'not displayed' as the reference category. The categorical predictor "transplant survival stratified" will be dummy coded (0=not stratified, 1=stratified), with 'stratified' as the reference category. The outcome variable "choice of hospital" will be dummy-coded (0=selective hospital, 1=non-selective hospital). The reference category is 'selective hospital'. Mediation analysis: The categorical predictor "total survival displayed" will be dummy coded (0=not displayed, 1=displayed), with 'not displayed' as the reference category. The categorical predictor "transplant survival stratified" will be dummy coded (0=not stratified, 1=stratified), with 'stratified' as the reference category. The categorical interaction term "total survival displayed\*transplant survival stratified" will be dummy coded (0=total and stratified information not displayed together, 1=both total and stratified information displayed together), with 'both' as the reference category. The continuous mediator variable "get any heart" will be mean-centered for each analysis. The outcome variable "choice of hospital" will be dummy-coded (0=selective hospital, 1=non-selective hospital). The reference category is 'selective hospital'.

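### The stated power of at least 90% does not describe the planned single-cell tests, which have about 85% power at two-sided 0.05; the tails and the comparison powered are not stated

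*Combined protocol and SAP*

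**What the plan says.** The Sample size rationale claims "at least 90% power to detect a 15 percentage point difference (e.g., 45% vs. 60%) between baseline condition 1 and the other 4 conditions", with alpha 0.05, and cites GPower. It names no test, no number of tails and no form of comparison. The Sample size section expects "approximately 200 participants per condition" out of a target of 1000. Inference criteria gives a 0.05 threshold, called standard, and does not mention sidedness.

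Hypothesis 1a says that a higher proportion of participants "will prefer the non-selective center over the selective center in conditions 2, 3, 4, and 5, relative to condition 1". Hypotheses 1b and 1c each name two conditions together (2 and 4; 3 and 4) against condition 1.

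The Analysis Plan tests Hypotheses 1a to 1d with one logistic regression on two binary factors, and "the model will also include an interaction term of these two variables". Each main effect is examined for whether it "is statistically significant and in the predicted positive direction". Study design limits this main analysis to conditions 1 to 4. Condition 5 is analysed separately, and the only test spelled out for it is "a contrast test for a difference in effect size between conditions 4 and 5".

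Transformations codes the stratification factor as "0=not stratified, 1=stratified), with 'stratified' as the reference category". Study design and Manipulated variables both give the combined (unstratified) display as the reference level.

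**The concern.** The power statement is the plan's only justification for its sample size, and whether it is true depends on the two inputs it leaves out. A reader who takes a standard 0.05 criterion as two-sided, and who sees that the planned coefficients compare single conditions, would conclude that each main-effect test misses a 15-point effect at most 10% of the time. At the plan's own example, the miss rate on that reading is about 15%. That matters when a non-significant main effect has to be interpreted.

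The reference label bears on the same issue. If stratified really were the reference level, the total-survival coefficient would no longer be a contrast with condition 1, and the power statement would not describe that coefficient at all.

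**Working it through.** **Inputs.** Rates 0.45 and 0.60, alpha 0.05 and claimed power of at least 90% (Sample size rationale); about 200 per condition (Sample size); a 2x2 logistic model with interaction (Analysis Plan) and 0/1 codes (Transformations). Sidedness is not given, so both readings are shown. All 200 per condition are assumed to be analysed.

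**What the coefficients compare.** With T = total survival displayed and S = stratified, logit(p) = b0 + b1·T + b2·S + b3·T·S. The cells are:
- condition 1: b0
- condition 2: b0 + b1
- condition 3: b0 + b2
- condition 4: b0 + b1 + b2 + b3

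So b1 is condition 2 versus 1 and b2 is condition 3 versus 1. Each is about 200 versus 200.

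**Formula.** Pooled-variance normal approximation: power = Φ[(d − z·SE0)/SE1], where d = 0.15, SE0 = √[p̄(1 − p̄)(1/n1 + 1/n2)], p̄ is the overall rate, and SE1 = √[0.45·0.55/n1 + 0.60·0.40/n2]. The critical value z is 1.960 two-sided and 1.645 one-sided.

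**Readings that reproduce the claim.**
- Pairwise, one-sided, 200 versus 200: p̄ = 0.525, SE0 = 0.04994, SE1 = 0.04937. (0.15 − 1.645 × 0.04994)/0.04937 = 1.374, so power is 91.5%.
- Pooled, two-sided, 200 versus 400: p̄ = 0.55, SE0 = 0.04308, SE1 = 0.04287. (0.15 − 1.960 × 0.04308)/0.04287 = 1.529, so power is 93.7%.
- Pooled, two-sided, 200 versus 800: p̄ = 0.57, SE0 = 0.03914, SE1 = 0.03921. (0.15 − 1.960 × 0.03914)/0.03921 = 1.869, so power is 96.9%.

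**Planned coefficients, two-sided.** 200 versus 200: (0.15 − 1.960 × 0.04994)/0.04937 = 1.056, so power is 85.4%.

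**Check against the test actually planned.** Summing exact binomial probabilities over the rejection region of the logistic Wald test for one single-cell contrast gives 85.6% two-sided and 91.4% one-sided. Also requiring a positive sign leaves the two-sided figure at 85.6%.

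**Sample size for 90%, pairwise two-sided.** n = [(1.960·√(2 × 0.525 × 0.475) + 1.282·√(0.2475 + 0.24))/0.15]² = 230.8, so 231 per condition, or 5 × 231 = 1155 in all. The exact Wald calculation gives 89.5% at 231 and first passes 90% at 235 (90.05%), or 5 × 235 = 1175.

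**Dependence on the example rates.** Two-sided pairwise power with 200 per condition, for a 15-point rise:

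| Rates | Power |
|---|---|
| 20% vs 35% | 92.2% |
| 25% vs 40% | 89.6% |
| 42.5% vs 57.5% (lowest) | 85.4% |
| 45% vs 60% | 85.4% |
| 60% vs 75% | 89.6% |
| 70% vs 85% | 95.2% |

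**Reference label.** If stratified were the reference, put S′ = 1 − S. Then logit(p) = (b0 + b2) + (b1 + b3)·T − b2·S′ − b3·T·S′. The total-survival coefficient becomes b1 + b3, which is condition 4 versus 3, and the stratification and interaction coefficients change sign. Hypothesis 1d predicts that condition 4 is not higher than condition 3, so that total-survival coefficient would be expected to lie near zero. The comparison is still about 200 versus 200, so the label does not alter the 85%. It alters what is being compared.

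**The case against.** The strongest reply is that the claim is correct as it stands. No section says the tests are two-sided. The hypotheses are directional and the Analysis Plan looks for effects in a predicted direction; one-sided, the pairwise power is 91.5%. Hypotheses 1b and 1c name two conditions against baseline, which can be read as 400 versus 200, with 93.7% power two-sided. The rates are also only an example, and they lie near the least favourable baseline.

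Much of this stands. A reader might infer that the investigators made an arithmetic error. The documents do not support that, because the stated figure can be reproduced on readings they leave open.

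The reply does not remove the mismatch. Asking for significance together with a predicted sign fits a two-sided test with a direction check equally well, and one-sided testing is nowhere declared. The pooled readings correspond to no planned model: the 0/1-coded interaction model estimates single-cell contrasts whatever the wording of Hypotheses 1b and 1c. Hypothesis 3 does imply a comparison of condition 5 with condition 1, but that would again be one single condition of about 200 against another.

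Two further inferences should be avoided. The 231 per condition depends on the formula, hence the range to 235. And the stopping rule ("Participants will be recruited until a sample size of 1000 is achieved") does not say whether exclusions are counted before or after the 1000 is reached. That is missing detail, not evidence of a further shortfall. As an assumed illustration only, 190 or 180 analysed per condition would give 83.6% or 81.6% two-sided.

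On the reference label, explicit 0/1 codes may well determine the fitted model, so the label may be a slip without effect. It still contradicts those codes and two other sections.

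**Conclusion.** The point holds as a mismatch between the stated power and the planned tests. For 45% versus 60% with 200 analysed per condition, each planned main-effect coefficient has about 85% power at two-sided 0.05, some 4 to 5 points below the stated minimum. This rests on reading the 0.05 criterion as two-sided, which is customary but not stated; if one-sided testing was intended, power is about 91% and there is no shortfall. It also rests on the plan's example rates, which lie close to the worst case for a 15-point difference. The consequence is modest and does not call the design into question, but the figure should be corrected or qualified because it is the only basis given for the sample size. The reference-category label is a separate, definite inconsistency.

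**What to change.** 1. **Sample size rationale.** State the GPower test, the tails and the comparison. For the tests as planned, restate the power as about 85% (two-sided 0.05, 200 analysed per condition, 45% versus 60%, each comparison of two single conditions).
2. **If one-sided testing was intended.** Declare it in Inference criteria before data collection, since it sets the rejection threshold, and report about 91% one-sided alongside the 85% two-sided figure.
3. **If the calculation was pooled.** Say so, and add the 85% that applies to the planned coefficients.
4. **Transformations.** Change the reference category of the stratification factor to not stratified (combined), in both the logistic and the mediation text. This agrees with the section's own 0/1 codes and with Study design and Manipulated variables, and makes both main-effect coefficients of the logistic model contrasts with condition 1.

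These are text changes. Recruitment and randomisation are unaffected, and the only cost is a slightly less favourable stated power.

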## Variables

Manipulated variables

We will manipulate how transplant center outcomes are presented. Different components of the same outcome statistics for two transplant centers will be varied over five different conditions. (1) Condition 1 ("baseline" condition): view only combined transplant survival (e.g. transplant survival rate not stratified by number and quality of donor hearts accepted at each center) (2) Condition 2: view combined transplant survival + total survival (e.g. overall survival rate at each center, computed from survival rates of both transplant and waitlist patients) (3) Condition 3: view only stratified transplant survival (e.g. transplant survival rate stratified into patients who received excellent donor organs and patients who received less than optimal donor organs) (4) Condition 4: view stratified transplant survival + total survival (5) Condition 5: view only total survival The first four conditions (1-4) will be included in our main analysis, which is a 2x2 design with 2 factors (total survival and transplant survival) and 2 levels per factor: (i) Total survival: "total not displayed" = reference level, in which only transplant survival rate (and no total or waitlist survival) is shown "total displayed" = transplant survival is displayed along with the overall survival rate at each center, which is computed from survival rates of both transplant and waitlist patients (ii) Transplant survival: "combined": reference level, in which transplant survival rate is not stratified by number and quality of donor hearts accepted at each center "stratified": transplant survival rate stratified into patients who received excellent donor organs and patients who received less than optimal donor organs The additional fifth condition, in which only total survival outcomes (and no transplant survival outcomes) are displayed, will be included in the study and analyzed separately.

Measured variables

The outcome variable will be a binary choice between two hospitals: one with a selective donor-heart acceptance strategy and one with a non-selective donor heart acceptance strategy. Participants will respond to the question "Which Hospital is a better choice for patients? Please click on one of the two tables below to indicate which hospital is the better choice." Participants will choose between two outcome tables featuring the selective and non-selective hospital (counterbalanced, such that each of the two choices is equally likely to be presented at top of the choice scenario in each condition). The number of participants that choose each hospital will be the measured outcome variable used in analyses. On the next page of the survey, participants will respond to three mediator questions: "There are many reasons why one transplant hospital might outperform another. Which reasons were most important in your decision? Please move the slider to indicate how much you considered each of the reasons below (0=reason was not important, 100=reason was extremely important)." Participants will then move a slider bar (0-100) to indicate the importance of the following three items: (1)

Patients were more likely to receive an excellent donor heart at the hospital I picked. (2) Patients were less likely to receive a marginal donor heart at the hospital I picked. (3) Patients were more likely to receive any kind of heart at the hospital I picked. The third item (more likely to receive any kind of heart) will be the only variable that is included in the planned mediation analysis.

Indices

*No response*

*No files selected*

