##### Inference criteria

We will use the standard  $p=0.05$  criteria for determining if the results are significantly different from those expected if the null hypothesis were correct.

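### Table position is counterbalanced by design but enters none of the planned models, so a small, nearly free precision gain is forgone

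*Combined protocol and SAP*

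**What the plan says.** The Variables section (Measured variables) describes a binary outcome. Participants click on one of two tables, one above the other, and the tables are "counterbalanced, such that each of the two choices is equally likely to be presented at top of the choice scenario in each condition".

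The planned analyses do not mention position again:

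- **H1 (Analysis Plan, Statistical models):** the predictors are the two display factors, and "the model will also include an interaction term of these two variables". No other term is named.
- **H2 (same section):** a causal mediation analysis with the display factors, the importance rating for getting any heart, and hospital choice. No covariate is named.
- **H3 (same section):** "we will use a binomial logistic regression analysis with a contrast test for a difference in effect size between conditions 4 and 5". No covariate is named.
- **Transformations:** codes the two display factors, their product, the mediator and the choice. Position is not coded.
- **Exploratory analysis:** left without a response.

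The Sample size rationale claims "at least 90% power to detect a 15 percentage point difference (e.g., 45% vs. 60%) between baseline condition 1 and the other 4 conditions", with alpha 0.05 and about 200 participants per condition.

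**The concern.** Counterbalancing suggests that the authors thought position could influence a click-to-choose response. Counterbalancing stops position from favouring one condition systematically. It does not remove the variation that position causes among participants within a condition. A model without position leaves that variation unexplained. In logistic regression, omitting a balanced factor that predicts the outcome also pulls the odds ratio towards 1.

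Position is assigned by the survey before the choice, so adjusting for it cannot introduce post-treatment bias. At stake is a modest amount of power for the display effects. Naming the term in advance also avoids a later discretionary decision about whether to adjust for position.

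**Working it through.** **Inputs from the documents.** Choice rates of 45% and 60% and alpha 0.05 (Sample size rationale); about 200 per condition (Sample size); position equally likely within condition (Measured variables).

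**Assumed.** The size of any position effect, because the documents give none. It is expressed as the gap g in choice of the non-selective hospital between that table on top and on the bottom, at 50% overall preference. On the logit scale this is b = 2 × ln[(0.5 + g/2)/(0.5 − g/2)]. The 45% and 60% are held fixed as averages over the two positions.

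**1. The plan's own figure.** For two proportions with pooled variance and 200 per arm:

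- Null SE = sqrt(0.525 × 0.475 × 2/200) = 0.0499; alternative SE = sqrt(0.2475/200 + 0.24/200) = 0.0494.
- Two-sided 0.05: power = Φ[(0.15 − 1.960 × 0.0499)/0.0494] = 85.4%.
- One-sided 0.05: 91.5%.
- Condition 1 against the other four pooled (200 vs 800), two-sided: 96.9%.

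The stated 90% is therefore met by a one-sided pairwise test or by the pooled comparison, but not by a two-sided pairwise test. The plan does not state sidedness. That is a separate matter; the two-sided pairwise case is used below.

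**2. Without the position term (logistic Wald test).** Log OR = ln(0.60/0.40) − ln(0.45/0.55) = 0.606. SE = sqrt[1/(200 × 0.2475) + 1/(200 × 0.24)] = 0.2026. Power = Φ(0.606/0.2026 − 1.96) = 84.9%.

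**3. With the position term.** For each gap, the two position-specific choice rates in each arm were found so that they average to 45% and 60%. The conditional log OR and its SE come from the information matrix of the model with arm and position.

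| Assumed gap g | Log OR | SE | Power | Gain (points) |
|---|---|---|---|---|
| 0 | 0.606 | 0.2026 | 84.9% | 0 |
| 10 points | 0.612 | 0.2037 | 85.2% | 0.3 |
| 20 points | 0.631 | 0.2070 | 86.2% | 1.3 |
| 30 points | 0.665 | 0.2131 | 87.8% | 2.9 |
| 40 points | 0.720 | 0.2225 | 89.9% | 5.0 |

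**4. Chance imbalance.** If position is drawn independently for each participant, the difference between two arms in the share with the non-selective table on top has SD sqrt(2 × 0.25/200) = 5 points. A 20-point gap then shifts the comparison by 0.05 × 20 = 1 point (1 SD). The sampling SE of the risk difference is 4.94 points, so this shift accounts for (1/4.94)² ≈ 4% of the variance. The position term at a 20-point gap lowers the variance of the risk difference by 3.9%. The two figures describe the same quantity.

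**5. Independent draws against forced 50:50.** These simulations (100,000 runs, 200 per arm) compare the unadjusted Wald test with a position-stratified Mantel-Haenszel test.

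| Gap | Position | Power, unadjusted | Power, stratified |
|---|---|---|---|
| 20 points | independent | 85.5% | 86.6% |
| 20 points | forced 50:50 | 86.1% | 86.5% |
| 30 points | independent | 85.4% | 88.3% |
| 30 points | forced 50:50 | 86.6% | 88.5% |

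For gaps up to 30 points, type I error of the unadjusted test was 4.9–5.1% with independent draws and 4.0–5.0% with forced balance. It was not inflated in either case.

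**The case against.** The strongest case against is that this is a preference and not a flaw. The design already deals with position by counterbalancing within condition. The planning rates are averages over position, so a position effect takes nothing from the power of the plan as written: the unadjusted 84.9% is the same at every gap. Gains well above 1 point need position alone to move choice by more than about 20 points, and nothing in the documents supports an effect of that size. The adjusted odds ratio also estimates a slightly different quantity, so adjustment is not entirely free.

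All of this stands, and it sets the size of the point. It does not make the adjustment wrong or contentious.

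A reader might infer three stronger things, none of which the documents support:

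- **That the condition comparisons are biased or the tests invalid.** The within-condition counterbalancing and the type I error results rule this out.
- **That uncorrected chance imbalance is a second harm on top of residual variation.** Step 4 shows that it is the same small quantity, and the unadjusted SE already covers it.
- **That position is certain to be unequal within conditions.** The plan does not say whether position is drawn independently or forced to 50:50. The simple randomization it describes concerns the five conditions. If position is forced to balance, imbalance can arise only from nonsense-response exclusions and incomplete surveys.

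The documents also do not say that position will be kept in the dataset, so recording it belongs in the fix.

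**Conclusion.** The point holds as a cheap improvement. Position is a counterbalanced design factor that no planned model uses, and the plan is valid without it. For 45% vs 60% with 200 per arm, two-sided, adjustment raises power from 84.9% to between 85.2% and 89.9% for assumed position gaps of 10 to 40 points. The gain is about 1 point at 20 points and nil if position has no effect.

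The result rests on an assumed position effect and on a two-sided pairwise test. It covers one two-condition comparison only. The gain for the H1 interaction, the H3 contrast and the H2 mediation effects was not computed.

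**What to change.** - **Variables and Transformations:** record the assigned table position for every participant and code it −0.5/+0.5 (non-selective table on bottom/top). State whether position is drawn independently or forced to 50:50 within condition.
- **Statistical models:** prespecify position as a covariate in the H1 and H3 logistic models. For H2, include it in both the mediator and the outcome model, so that both condition on the same factor.
- **Reporting:** give raw choice proportions and position counts by condition.

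The cost is one recorded variable and one term per model, with no extra participants. The odds ratio becomes conditional on position (log OR about 0.63 against 0.61 at a 20-point gap), so the unadjusted proportions should be shown beside it. A lighter alternative is to keep the planned models and prespecify the position-adjusted ones as a sensitivity analysis.

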only is displayed (condition 3). Hypothesis 2: There will be an indirect (mediated) effect of providing participants with information about stratified transplant survival or total survival; this information will lead to higher preference for the non-selective hospital by leading participants to think that the chances a patient at either hospital will "get a heart at all" is a more important factor in their decision (about which hospital is a better choice for patients). Specifically ratings of importance (0-100 continuous scale) for the item "likelihood of getting any heart" will differ across conditions 1-4 such that "getting any heart" will be rated lower in condition 1 than in the other three conditions. Furthermore, ratings on this item will be associated with choice, such that higher ratings will be associated with choice of the non-selective center. Hypothesis 3: Participants who view total survival only (condition 5) will show a higher preference for the non-selective center relative to participants in the baseline combined transplant survival display (condition 1) such that the effect of displayed total survival alone will be similar to the effect of displaying both stratified transplant survival and total survival outcomes together (as in condition 4).

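### The only H2 mediator is rated after the hospital choice and refers to the chosen hospital, yet a significant ACME is to be read as the mechanism behind the choice

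*Combined protocol and SAP*

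**What the plan says.** **Timing and wording.** Under Variables (Measured variables), the outcome is a click on one of two hospital tables. Then, "On the next page of the survey, participants will respond to three mediator questions". The third item, "Patients were more likely to receive any kind of heart at the hospital I picked", is the only one that enters the mediation analysis.

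**Hypothesis.** H2 says the displays raise preference for the non-selective hospital "by leading participants to think that the chances a patient at either hospital will" receive any heart is a weightier factor. It makes two specific predictions: the rating "will be rated lower in condition 1 than in the other three conditions", and "ratings on this item will be associated with choice".

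**Analysis and interpretation.** Analysis Plan (Statistical models) states: "we will conduct a causal mediation analysis to determine whether information display had a mechanistic effect on hospital choice through our proposed mediator". There the mediator is the importance of getting any heart "at each hospital when considering the choice". A significant ACME "would suggest that displaying total survival works via increasing the perceived importance of" getting any heart, and the same reading is given for the stratified display and for the combination. If the ACME is not significant, the plan undertakes to locate the break in the causal path. The proportion mediated is also defined.

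**The concern.** The variable treated as a cause of the choice is recorded after the choice, and its content refers to what was chosen. Someone who has just picked a hospital may rate reasons so as to justify the pick. In that case the path is display → choice → rating, and not display → rating → choice. Only the display is randomised, so both paths produce a rating that differs by condition and is associated with choice.

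The Description says the mediator is there to identify the decision process behind the choice. A significant ACME and a proportion mediated that came from post-choice justification would be reported as that process. The stake is the causal reading of H2. The effect of display on choice (H1 and H3) is a randomised comparison and does not depend on the sliders.

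**Working it through.** The plan gives no figure on this point to reproduce. The check has two parts.

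**1. The passages side by side**

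- *Order:* choice first, rating on the following page (Measured variables).
- *Referent:* either hospital (Hypotheses), each hospital (Statistical models), the chosen hospital (the item itself). The first two are choice-neutral; the item is not.
- *Built-in dependence:* by design (Description) the non-selective hospital takes all donor offers and the selective one tends to decline those below excellent. The item's premise therefore fits one choice and not the other. A participant who chose the selective hospital has reason to rate it low even if the chance of any heart did weigh in the decision.
- *Caveats:* the mediator is called putative, proposed and hypothesised. No section mentions timing, reverse direction, the assumptions behind a causal ACME, or a sensitivity analysis. The Exploratory analysis section is empty.

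**2. How often the planned rule finds a mechanism when there is none**

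Inputs from the plan: choice of the non-selective hospital 45% against 60% (Sample size rationale); about 200 per condition (Sample size). Inputs assumed, because the documents do not give them: rating SD 25 or 30, and the rating gap between the two groups of choosers, 0 to 40 points.

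Model with zero mediation, one display condition (T = 1) against condition 1 (T = 0):

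- choice Y depends on T only;
- rating M = 50 + gap × (Y − 0.5) + Normal(0, SD), clipped to 0–100.

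Analysis: M linear in T; logit P(Y = 1) linear in T and M; ACME = mean over t = 0, 1 of E[P(Y = 1 | t, M(1))] − E[P(Y = 1 | t, M(0))]; percentile bootstrap with 200 resamples; 2000 trials per setting (Monte Carlo SE up to 1.1 points). The joint test requires a higher rating in the display arm and a higher rating in non-selective choosers, each by t test at two-sided p < 0.05.

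| Gap | ACME significantly positive, SD 30 / SD 25 | Both H2 predictions met, SD 30 / SD 25 | Mean ACME ÷ mean total effect, SD 30 / SD 25 |
|---|---|---|---|
| 0 | 0.0% / 0.1% | 0.1% / 0.1% | – |
| 5 | 1.8% / 2.6% | 2.4% / 3.0% | – |
| 10 | 6.8% / 8.8% | 5.9% / 7.6% | 2.6% / 3.7% |
| 20 | 16.5% / 22.6% | 14.9% / 19.9% | 9.3% / 13.4% |
| 30 | 31.5% / 38.8% | 29.2% / 36.6% | 19.5% / 25.6% |
| 40 | 41.7% / 50.4% | 39.4% / 48.2% | 29.1% / 37.7% |

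The nominal rate for a significantly positive ACME is 2.5%. A shorter repeat (400 trials per setting, SE up to 2.5 points) gave 0%, 7–10%, 17–23% and 40–53% at gaps 0, 10, 20 and 40.

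*Hand check of the joint test, gap 20, SD 25, ignoring clipping.*

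- Rating difference between arms = 20 × (0.60 − 0.45) = 3 points.
- Variances = 625 + 400 × 0.45 × 0.55 = 724 and 625 + 400 × 0.60 × 0.40 = 721.
- SE = √((724 + 721)/200) = 2.69, so the difference is 3/2.69 = 1.12 SE.
- P(Z > 1.96 − 1.12) = P(Z > 0.84) ≈ 0.20.
- Expected choosers: 90 + 120 = 210 non-selective and 190 selective. The rating–choice link is 20/(25 × √(1/210 + 1/190)) = 20/2.50 ≈ 8 SE, so it is practically always significant.
- The joint rate is therefore about 20%, against 19.9% simulated.

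**The case against.** *Asking for reasons after the choice is sensible.* A question about getting any heart placed before the choice could prime it and contaminate H1 and H3. This stands, and it is why the order should stay.

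*The wording is hedged, and the slider stem asks how much each reason was considered, which fits the Analysis Plan's description of importance at the time of choosing.* Also true. The rating may well carry genuine pre-choice reasoning, and the documents cannot settle how much. But the hedges express general uncertainty. None concerns direction, and the mismatch between either or each hospital and the chosen one remains.

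*The simulation is a worst case.* It makes the rating wholly a consequence of choice, whereas the concern is that it may be partly so. The gap and SD are assumed, and clipping shrinks a nominal gap of 20 to about 18–19 and of 40 to about 35–37. It uses two arms of 200, whereas the plan codes three display terms across conditions 1–4 (about 800 people). These points limit how literally the percentages can be taken. They do not alter the finding that a purely choice-driven rating can produce a positive, significant ACME.

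*Rewording the item does not remove post-choice justification, and it shifts the construct from a comparative reason to general importance.* Both are correct. Rewording aligns the item with H2; the limit on interpretation has to come from the text.

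**Conclusion.** The concern holds and should be fixed. The sole mediator follows the outcome in time and is worded in terms of it, and the pre-specified interpretation assumes one causal direction without saying so.

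The size depends on how far choosing shifts the rating. At 5 points or less the problem is minor: the false-mechanism rate is 1.8–2.6%, about nominal. From about 20 points it is material: 16.5–22.6% false mechanisms with a spurious proportion mediated of 9–13%. At 40 points these become 41.7–50.4% and 29–38%. All of this rests on the assumed SD and gap and on a true display effect of 15 percentage points.

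H2's two specific predictions remain testable as a comparison and an association. Taken together they share the weakness, since with no mediation both come out significant nearly as often as the ACME does at gaps of 10 points and above. H1 and H3 stand.

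**What to change.** 1. **Before data collection, make item 3 choice-neutral** so that it matches H2, for example: *How important was a patient's chance of receiving any donor heart at all?* Reword items 1 and 2 in parallel, and reconcile Hypotheses, Measured variables and Statistical models on which hospital the item refers to.
2. **Keep the choice first and change the interpretation.** Report the ACME and proportion mediated as associational. Replace the mechanistic and works-via language, and the promise to find the break in the causal path, with: *A significant ACME is consistent with the display raising the stated importance of getting any heart; importance was rated after the choice, so the reverse direction cannot be excluded.*
3. **Keep H2's two predictions as a comparison (rating by condition) and an association (rating with choice) only**, adding: *Together these two results have the same limitation as the ACME and do not establish mediation.*

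The cost is three slider items and a few sentences, with no extra participants, no change in question order and no change to H1 or H3. The downside is a weaker claim for H2. This corrects what may be concluded; it does not supply a test that separates the two directions. The Existing Data section places registration before data creation, so the item can be changed at that stage. Once collection has begun, only parts 2 and 3 remain open.
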